#### **5.1.4 Vulnerable Subjects**

*Note: this study includes surveys and interviews only, no clinical interventions.)*

### **VA Patients**

As this study is an effectiveness trial conducted under real-world implementation conditions, we will conduct the study in those who 1) are eligible to participate in SMAs, and 2) who can give informed consent. This excluded individuals with impaired decision-making capacity, those who do not speak English proficiently, and prisoners. It includes all other groups. There are no interventions as part of this study, so we will not exclude pregnant women.

### **VA Employees**

Employees will be included for interviews and observations to gain knowledge regarding implementation of SMAs and the P2P program.

## **5.2 Recruitment Methods**

At a minimum, we will require 560 VA patients in the SMA and SMA+P2P groups and 560 VA patients in the control group (see power calculation in Section 5.6.1 below). We will also enroll up to 56 VA employees.

### **VA Patients**

SMA and SMA+P2P groups – As *usual care*, some sites may only conduct one group at a time depending on variability of their resources over time, but all sites will conduct a number of groups over the study period and the two treatments will be offered in a random sequence within site. Patients are not assigned to groups, but are recruited from a population of eligible patients when the site is ready to run a new group. Thus patients will be randomly sampled for invitation from eligible patients and recruited for each wave of the group treatment with a standard script that is identical whether the group is SMA only or whether P2P will be offered as an additional optional part of the intervention. There will be two methods of recruitment: existing mechanisms and data pull.

#### **Existing Mechanisms**

During the start-up period of this project, many of the participating sites established a strong referral base and high participation rate in their SMAs. All patients referred to SMAs will be scheduled into the next available SMA; the scheduler will not be aware of which SMA groups will be offering P2P as an additional optional component. Once the patient is scheduled, the scheduler will communicate the patient's information to the RC through encrypted email, CPRS alert, or a phone call.

All patients scheduled for an SMA who meet our eligibility criteria will be mailed the Study Intro Letter, the Study Info Letter, a HIPAA authorization, and the baseline survey. Participants will be asked to return the baseline survey (with a waiver of written informed consent) prior to attending their first SMA, and the signed HIPAA authorization prior to the study team linking medical record data to the survey data. The RC may call participants who have not returned the baseline survey and/or HIPAA prior to the first SMA. Whenever possible, the RC will attend the first SMA in order to administer/collect any outstanding baseline surveys and/or HIPAAs for those interested in the study, and distribute incentives for completion. Depending upon what type of group is starting at the time the participants are starting SMAs, they will become part of the **SMA group** or the **SMA + P2P group**.

#### **Data Pull**

Each quarter, the Data Manager will pull a list of all patients meeting the eligibility criteria outlined below. At our Ann Arbor site and Palo Alto site and subsites, the RC will provide

each newly eligible patient's assigned provider (PCP or RN) the opportunity to opt that patient out of SMA recruitment. Providers will be asked to respond within 1 week and at that point, any patients who were not opted-out will be recruited.

Eligible patients will be sent an SMA Info Letter explaining that they are being invited to participate in SMAs, provided a brief description of what the SMAs involve, and informed that some groups will also be offered an additional (optional) opportunity to participate in P2P as a supplement to the SMAs. This introductory letter will also explain that they will be asked if they are interested in participating in a research study to evaluate this program. It will explain that they may participate in the SMAs regardless of their decision to participate in the research study. It will also include a phone number to call to opt-out of the invitation to participate in the research study, or to opt-out of both the invitation to participate in SMAs and the research study. Unless patients respond that they do not wish to participate, the letters will be followed with a phone call to further describe the program. If patients are interested in participating, they will also be asked a set of brief screening questions to screen out people with active substance abuse. Then the RC will schedule the patient to attend an upcoming SMA or SMA + P2P meeting. Veterans who do not wish to participate will be replaced with another Veteran randomly selected from the population of eligible Veterans, until the SMA group is filled. A full group will range from 10 – 14 patients depending upon the site resources.

The patients who elect to participate in the SMAs will be asked if they are interested in participating in the study. If they are interested in the study, they will be asked to sign a HIPAA authorization to collect their medical record data and link it to survey information collected as part of the study in order to evaluate the SMA program. Even if they decide not to participate in the evaluation, they can still participate in the programs. Those who are interested in the study will be sent a BL Packet Letter, the Study Info Letter, a HIPAA authorization, and the baseline survey. Participants will be asked to return the baseline survey (with a waiver of written informed consent) prior to attending their first SMA, and the signed HIPAA authorization prior to the study team linking medical record data to the survey data. The RC may call participants who have not returned the baseline survey and/or HIPAA prior to the first SMA. Whenever possible, the RC will attend the first SMA in order to administer/collect any outstanding baseline surveys and/or HIPAAs and distribute incentives for completion. Depending upon what type of group is starting at the time the participants are starting SMAs, they will become part of the **SMA group** or the **SMA + P2P group**.

Follow-up surveys, along with a pre-stamped business reply envelope, will be mailed to participants at 6-months and 12-months after their first SMA. Participants who do not return a completed survey will be mailed a second survey 2 weeks after the initial mailing. RAs may follow up by phone with participants who have outstanding surveys.

A random sample of the participants who participate in the P2P program, stratified by participation level, will be asked to participate in a semi-structured telephone interview to better understand their experiences with the program. At the end of the program, patients will be stratified by participation level: the **low participation group** (began the intervention but completed fewer than 25% of weekly phone calls/group sessions in 12 months of program participation); **moderate participation group** (completed approximately 50% of weekly phone calls/group sessions); and the **significant participation group** (completed greater than 75% of weekly phone calls/group sessions). Study staff will attempt to interview, by phone, an equal number of participants in each of these 3 groups.

The patients who are invited but decline participation in the P2P (**declined participation group**) will be asked if they are willing to answer a few questions with a study team member. The responses will be recorded but there will be no link between the responses and the participant.

Of the patients receiving usual care who were randomly not selected for invitation SMAs (since in all the sites too many patients will be eligible for invitation than there are resources to accommodate over the study period), a random sample will be selected from each wave to be part of the **no intervention control group** under a waiver of informed consent.

Patients will receive a \$20 gift card upon completion of the baseline survey and a \$10 gift card will be mailed with both the 6 and 12-month survey. Additionally, Patients who participate in an interview will receive a \$10 gift card by mail.

### **VA Employees**

Members of the Ann Arbor study team will send an introductory email with an attached information letter to these potential participants explaining the study. This email will give them an option to call to opt-out. Those who do not opt-out will be contacted by the RAs or [name] and will be asked if they are willing to participate. Employees who do not opt-out may also be approached in-person at the time of an observation. Verbal informed consent will be obtained from those willing to participate, and an appointment to complete the interview/observation will be scheduled. Verbal informed consent will also be captured at the beginning of recorded interviews.

## **5.3 Informed Consent Procedures**

### *Informed Consent will not be sought for*

- *Veterans randomly selected from those who have not been asked to participate in SMAs (inactive controls). There will be no contact with this group.*
- *Veterans who are invited to participate in SMA or P2P but elect not to (declined participation group). We would like to ask them a few questions at the time that they elect not to participate or soon after by telephone in order to better understand the barriers to participating in the program. (Appendix 3, Refuser Questions)*

### *Request Waiver of Documentation of informed consent*

- *Veterans in the SMA and SMA+P2P groups.*

*Veterans who are interested in the research study will be asked for verbal informed consent. Those who provide verbal informed consent will be sent a study survey by mail, as well as an information letter about the study, a HIPAA authorization request, and a postage paid return envelope. This will allow participants to complete the baseline study survey at home, eliminating the inconvenience of needing to come in early to a clinical appointment to complete the consent process and paper survey just prior to their first SMA.*

*Until a signed HIPAA authorization is returned, survey/interview data will not be linked to PHI collected from administrative/medical record data. The RC may call participants who have not returned a signed HIPAA prior to the first SMA. The RC may also attend the first SMA to administer/collect any outstanding HIPAAAs. If a signed HIPAA has not been returned at the time that the follow-up surveys are mailed, an additional HIPAA will be included in the mailing.*

- *Employees.*

*Employees will be e-mailed an introductory letter, including an information sheet about the study. Those who are interested in participating will be asked to provide verbal informed consent.*

Training will be conducted with each study team member approved to obtain informed consent at each recruiting site. This training will be conducted by telephone by the Ann Arbor project manager. In addition to this structured training, informed consent procedures will be reviewed with all study staff at the regularly study meetings, which will include discussion of the events of

the week where we will answer questions and address any problems/events to reduce the likelihood of occurrence in the future.

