As SMAs are being implemented as part of usual care, resources will not permit all patients

eligible for the program to be invited. Of those patients who are not invited to participate, a random sample will be identified from each site to serve as an untreated control (usual care without SMAs). We request a waiver of informed consent and HIPPA authorization for these patients in order to collect laboratory and service utilization data solely for research purposes.

Semi-structured interviews with five to eight key informants (VA staff) at the participating sites will be conducted to obtain information on CFIR constructs likely to influence implementation success. These interviews will include the director of primary care, clinicians participating in the SMAs, P2P group facilitators, and other key staff involved in diabetes patient care (e.g., nurses, dieticians, pharmacists).

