### **5.6.1 Analysis Plans by Aim**

Aim 1 (Evaluation of the effect of SMAs and SMAs+P2P compared to usual care on diabetes patients' glycemic control, blood pressure, statin use, and insulin starts at 6 and 12-18 months post-enrollment): The primary analysis will be an intention to treat analysis (ITT) comparing all participants scheduled for an SMA (regardless of whether an SMA was actually attended) and eligible patients randomized to usual care. We also will conduct analyses comparing outcomes between the usual care group and: 1) The SMA Attendee group, defined as a subset of those in the SMA ITT group who attended at least one SMA; and 2) the SMA Engagement group, defined as the subset of patients who attended at least half of the SMAs offered in the series.

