Aim 2 (Assessment of the impact of SMAs and SMAs+P2P on service utilization and patient-centered outcomes, including patients' satisfaction with VA care, diabetes-specific quality of life and social support at 6 and 12 months post-enrollment). In our analysis of changes in patient-centered outcomes as reported on patient surveys, we will conduct a paired Wilcoxon signed rank test to determine if there are significant changes between baseline and the 6- and 12-month post-enrollment evaluation periods. We will use the Benjamini-Hochberg (BH) procedure to attempt to control the false discovery rate due to the multiple comparisons. There were very few participants in the SMA+P2P group chose to be formally matched with another participant in their SMA to give and receive peer support outside the SMA. If we do not have sufficient sample size of participants in P2P, we will be unable to compare outcomes between the SMA-only and SMA+P2P arms. In that case, will only conduct our primary analysis that combines the two SMA groups (SMA-only and SMA+P2P) into one active treatment group and compare clinical outcomes of participants participating in SMAs with those in usual care.

Fidelity of the P2P Program. To collect data on fidelity, checklists of key content areas to cover and communication skills that should be used will be completed and forwarded to Ann Arbor. A HBC or another qualified health behaviorist will attend the first P2P visit (immediately following the first SMA) and will complete a fidelity assessment checklist. Additionally, they will provide feedback to the P2P facilitator immediately following the session. This feedback will be documented and shared with the Ann Arbor study team. An assessor will continue to attend drop-in sessions, completing fidelity assessments and providing feedback, until he/she feels the P2P facilitator is ready to continue without assistance. Then the fidelity assessments will be completed approximately every 3rd drop-in session for the remainder of the study. Additionally, the P2P facilitators will be asked to complete self-assessment checklists after each session which will be forwarded to Ann Arbor.

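### With no cut-off for signed authorization, the primary SMA set is likely, though not shown, to over-represent attenders and survey responders

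*Combined protocol and SAP*

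**What the plan says.** The primary analysis in section 5.6.1 (Aim 1) is called intention to treat, "comparing all participants scheduled for an SMA (regardless of whether an SMA was actually attended"), against usual care. Attendee and Engagement subsets are defined separately.

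An SMA or SMA+P2P patient comes into the research data through a HIPAA form. Section 5.2 (Data Pull) says of patients interested in the study that "they will be asked to sign a HIPAA authorization to collect their medical record data and link it to survey information". The form and the baseline survey are requested before the first SMA, and the research coordinator (RC) may telephone people whose papers are outstanding. Two later routes remain open:

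- At the first session, section 5.2 (Existing Mechanisms): "Whenever possible, the RC will attend the first SMA in order to administer/collect any outstanding baseline surveys and/or HIPAAs for those interested in the study".
- At follow-up, section 5.3: "If a signed HIPAA has not been returned at the time that the follow-up surveys are mailed, an additional HIPAA will be included". Section 5.2 (Data Pull) says these surveys are "mailed to participants at 6-months and 12-months after their first SMA".

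Controls are handled differently. Section 5.1.1 states "We request a waiver of informed consent and HIPPA authorization for these patients", and section 5.3 adds "There will be no contact with this group".

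On when the arm becomes apparent, section 5.6.1 (Fidelity of the P2P Program) says that a health behaviorist "will attend the first P2P visit (immediately following the first SMA").

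**The concern.** An intention-to-treat set should be fixed by something that happens before treatment. Here a scheduled patient's place in it may depend on turning up at the first session or answering a mailing months later. Controls pass no such filter. If people who attend and respond also have better A1c trajectories, the set drifts toward the Attendee subset from which the plan means to keep it distinct, and the SMA versus usual-care estimate moves in favour of SMA.

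Two further consequences follow. In SMA versus SMA+P2P, a signature given once the arm is known can differ by arm. The identical script, the random sampling for invitation and the scheduler's unawareness of group type all act earlier and do not protect against this. In Aim 2, the paired tests of survey change need a baseline taken before the intervention begins.

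**Working it through.** **1. The texts side by side.** Section 5.2 (Data Pull) ties the form to collecting the record data as well as linking them. Section 5.1.1 requests the authorization waiver for controls only. Together these imply that the form gates an SMA patient's record outcomes. Section 5.2 (Existing Mechanisms) and section 5.3, however, speak only of linking survey data to record data. No section sets a closing date for authorization, plans an analysis by signing date, or says whether the scheduled set means every scheduled patient or only those who signed. The imputation in section 5.6.1 deals with missing outcomes and does not mention patients who never sign.

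**2. The plan's own figures.** The plan gives no attendance, survey-return or authorization rate, so there is no stated figure for this filter to reproduce. Section 5.6.2 supplies the yardsticks: a 0.5-point A1c target, an SD of change of 1.45, an ICC up to 0.10 in the active arm and 0 in controls, and a minimum of 560 per side. The 560 reproduces as 7 sites × 10 groups × 8 people.

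**3. Illustration (all inputs assumed).** Of 100 scheduled patients, 50 sign by mail before the first SMA. Attendance is 70% in both halves, so the mail signers are 35 attenders and 15 non-attenders. Of the other 35 attenders, 60% sign at the session: 0.60 × 35 = 21. A fraction *s* of the other 15 non-attenders signs by telephone prompt or later mailing. Attenders' A1c change is 0.5 to 1.0 points better.

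Attender share = (35 + 21) / (50 + 21 + 15*s*). Shift = (share − 0.70) × difference.

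| *s* | Set | Attender share | Shift at 0.5 | Shift at 1.0 |
|---|---|---|---|---|
| 0 | 71 | 56/71 = 78.9% | 0.04 | 0.09 |
| 0.30 | 75.5 | 56/75.5 = 74.2% | 0.02 | 0.04 |
| 0.60 | 80 | 56/80 = 70.0% | 0 | 0 |

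**4. Dependence on the inputs.** Let attendance be *a*, with signing rates *p* in attenders and *q* in non-attenders. Then share = *ap* / (*ap* + (1 − *a*)*q*).

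- With *a* = 0.70, *p* = 0.90, *q* = 0.50: 0.63/0.78 = 80.8%. A 0.5-point difference gives a shift of 0.108 × 0.5 = 0.054.
- The standard error at 560 per side, groups of 8 and ICC 0.10 is 1.45 × √((1 + 7 × 0.10)/560 + 1/560) = 0.101. If the attenders' advantage is purely prognostic, two-sided type I error is about 0.083 instead of 0.05 (normal approximation; the 0.05 level is assumed, as the documents give none).
- Over *a* = 0.60 to 0.80, *p* = 0.90, *q* = 0.30 to 0.90 and differences of 0.3 to 0.8, the shift runs from 0 to 0.175. It is 0 whenever *q* = *p*.

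**5. Timing against disclosure.** At 6 and 12 months the patient knows whether P2P was offered. At the first session the order is not stated: P2P follows the SMA, but the text does not say whether papers are collected before or after the offer.

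**6. Baseline.** The survey is due before the first SMA, but one taken at that session may be completed during or after it.

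**The case against.** The strongest reply is that the form may not gate the record data at all. Two of the three places that describe its effect mention only linkage. If records are used for every scheduled patient, the primary A1c set is untouched. This stands as an ambiguity, but the wording about collection and the controls-only waiver point the other way, so the plan needs to say which is meant.

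Second, non-attenders are not shut out. The RC can telephone them before the first SMA, and a repeat form by mail might recover some and dilute the imbalance. This also stands, and it is why the range includes zero. It is weakened because follow-up mailings are timed from a first SMA, which leaves no stated date for someone who never attended.

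Third, a late signature is largely paperwork: follow-up surveys go to existing participants, and section 5.3 places verbal consent before the packet. That is fair, but their record outcomes may still become usable only because they responded late.

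A reader might infer more: that the primary set is demonstrably enriched, that patients signing at the first SMA already knew their arm, or that disclosure of the arm biases the primary comparison. The documents support none of these. They give no rates and do not fix the order of events at the session. The primary comparison in section 5.6.1 takes everyone scheduled for an SMA against usual care, so knowing the type of group bears mainly on SMA versus SMA+P2P. Section 5.6.1 says that comparison will be dropped if too few take up P2P.

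**Conclusion.** The point holds as a likely, unquantified selection and a gap in definition. If the form gates record data, membership of a set described as independent of attendance can depend on attending or responding, while controls face no such condition. On the inputs in step 3 the shift toward SMA is 0 to 0.09 A1c points, at most 18% of the 0.5-point target (0.09/0.5). The wider assumptions in step 4 reach 0.175. All of these rest on assumed rates and an assumed difference in A1c change between attenders and non-attenders. The shift is zero if the two sign equally often. The risk from late signing by arm is confined mainly to SMA versus SMA+P2P, and the baseline problem to surveys completed during or after the first session.

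**What to change.** 1. In section 5.6.1, define the intention-to-treat set by scheduling. Reconcile sections 5.2 and 5.3 on whether the form gates use of record data or only linkage. Tabulate authorization by date, attendance and arm, with all scheduled patients as the denominator.
2. Add a sensitivity analysis of the primary A1c comparison restricted to patients whose authorization is dated before the day of the first SMA. The cut-off has to precede that day, because forms signed at the door still reach only those who come. This should not become the primary set: in the illustration it would drop 21 of 71 patients (30%) and leave mainly mail responders.
3. In section 5.2, have the RC collect outstanding surveys and forms before the first session opens and before the group hears whether P2P is offered. Do not use any survey dated after that point as baseline.

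The cost is some lost late baseline surveys and a little more analysis, using dates on papers already collected. These changes do not remove the broader selection of volunteers relative to controls who were never contacted, which should be acknowledged as a limitation.
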